2.2.6.7.2 IMRT Treatments

In general, *for both groups*, IMRT (XRT) must start no more than 24 days after marking/ implantation. Sites will perform a weekly positioning verification using Cone beam or low dose CT scan. For the *Balloon Group*, scan results will also be used to verify balloon spacing of at least 10 mm. Subjects will receive IMRT based on the sites' dose-fractionation schedule. The following data will be captured for *both groups* during the last day of a weekly visit, for as many weeks as the treatment lasts:

IMRT Data Collection:

This data should be captured once per week on the last day of that weeks' treatment sessions during active IMRT treatment.

Weekly

- For *Balloon Group* verification of spacing status as at least 10 mm (from prostate to rectum);
- Changes in medications;
- Expanded Prostate Cancer Index (EPIC) assessment (done once at mid-point assuming the treatment plan exceeds one month (4 weeks));
- Perineal access site healing status (until healed) and
- Adverse events as defined by Sections 2.3.6 and 2.3.7 of this Protocol.

Last XRT Visit

- CT scan taken as described in Section 2.2.4 for the *Balloon*;
- Changes in medications;
- Expanded Prostate Cancer Index (EPIC) assessment and
- Adverse events as defined by Sections 2.3.6 and 2.3.7 of this Protocol.

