2.3.4.5 SECONDARY ENDPOINTS

Secondary Safety endpoints include:

- The rate of Grade 2 or greater rectal or implantation procedure related adverse events with a duration of at least 5 days and implantation procedure related adverse events in the *Balloon Group* subjects compared to *Control Group* subjects in the 6 month follow-up period post marking and/or balloon implantation.
- Degree of all GU acute toxicity as determined by the Expanded Prostate Cancer Index Composite (EPIC).

The adverse event endpoint will be analyzed using a Fisher's Exact test. The EPIC endpoint will be modeled by visit using a repeated measures model with an unstructured covariance matrix.

Secondary efficacy endpoints include:

- Additional dosimetry parameters (D_{Rectum}100, D_{Rectum}90, D_{Rectum}80, D_{Rectum}70) will be evaluated in the balloon arm only, where subjects will serve as their own control (dosimetry reduction after balloon implantation) as the dosimetry parameters are compared to their baseline values per subject.
- Core lab evaluation of distance of rectal wall from the prostate at baseline and last XRT visit. This data will be measured and quantified.

These are all numeric measures and will be compared between groups using Rank-Sum tests.

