#### **Handling of Missing Data**

The handling of missing data from the primary safety and efficacy analyses is addressed through the sensitivity analyses identified in Sections 10.3.4.1.3 and 10.3.4.2.3. All other summaries will be based on available data, without imputation of missing data.

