#### Secondary Safety Endpoint #2: EPIC Scores

An additional secondary safety endpoint concerns the degree of all GU acute toxicity as determined by the Expanded Prostate Cancer Index Composite (EPIC). The version used in this study was the EPIC-26 short form. EPIC scores range from 0 to 100 (transformed from Likert scale responses), with higher scores indicative of better functioning. For each of four EPIC domains (Urinary Incontinence, Urinary Irritative, Bowel, and Sexual), the analysis of the EPIC endpoint will evaluate change in EPIC score over time.

<sup>3 Wei JT, Dunn RL, Litwin MS, Sandler HM, Sanda MG. Development and validation of the expanded prostate cancer index composite (EPIC) for comprehensive assessment of health-related quality of life in men with prostate cancer. Urology. 2000;56(6):899-905.

Statistical Analysis Dlan	Client/Project	BioProtect BP-007
Statistical Allalysis Flan	Version and Date	V2 05-DEC-2021

The domain scores will be summarized descriptively by visit and group along with the change from baseline. Non-parametric Rank-Sum tests will be used to compare change from baseline between groups for each domain at the IMRT midpoint and IMRT final visit.

In addition, for each domain, change from baseline in EPIC score over the course of the study will be evaluated using a mixed model. The independent variables will include visit, treatment group and visitby-treatment group interaction as factors, continuous baseline EPIC score as a covariate and Subject as a random effect. The model will used with an unstructured covariance matrix. In case it fails to converge, a compound symmetry covariance matrix will be used. Least Squares Means will be used to estimate between-group differences for each visit. Type III tests for the factors will be provided.

In addition, change in EPIC score from Screening to the end of IMRT will be analyzed using a separate analysis. The timing of the final IMRT visit is not fixed across subjects, and therefore, cannot be considered as part of the mixed model described above.

This endpoint will be analyzed using the following regression:

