#### *Change in EPIC = Baseline EPIC + Group*

The residuals of all linear or mixed model will be evaluated to consider the degree to which the data appear to be normally distribution.

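### The SAP's reason for leaving the final IMRT visit out of the EPIC mixed model does not hold; adding that visit costs almost nothing, though the expected gain is small

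*SAP*

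**What the plan says.** Protocol 2.3.4.5 specifies for this endpoint: "The EPIC endpoint will be modeled by visit using a repeated measures model with an unstructured covariance matrix". It names no visit to be left out. Protocol 2.3.3 also lists EPIC on the last day of IMRT, tested by a two-sided Rank-Sum test, among the three analyses that may support labelling.

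SAP 10.3.5.1 plans three things for each of four EPIC domains:

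- Rank-Sum tests of change from baseline between groups at the IMRT midpoint and at the final IMRT visit.
- A mixed model for change over the study: "The independent variables will include visit, treatment group and visitby-treatment group interaction as factors", with baseline score as a covariate and subject as a random effect. On covariance: "The model will used with an unstructured covariance matrix", with compound symmetry if that does not converge. The visits in the model are not listed.
- For the final IMRT visit, "change in EPIC score from Screening to the end of IMRT will be analyzed using a separate analysis", because "The timing of the final IMRT visit is not fixed across subjects, and therefore, cannot be considered as part of the mixed model". The regression is "Change in EPIC = Baseline EPIC + Group".

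Secondary analyses use the Per-Protocol population (SAP 10.3.5). On missing values outside the co-primary endpoints, SAP 10.1 says: "All other summaries will be based on available data, without imputation of missing data". The only EPIC item among the changes in SAP 3.2 is the choice of four domains.

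**The concern.** Variable timing would matter if time entered as a continuous variable, or if the covariance depended on the spacing of visits. Neither is so here. The stated obstacle is therefore not an obstacle, and applied consistently it would also remove the midpoint score.

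Two things follow. The model's visit-by-group interaction, Type III tests and least-squares means do not cover the end of radiotherapy, the day the Protocol chose for its EPIC labelling test of acute toxicity. And the regression for that day sets aside the midpoint score, which is the best available information on men whose final score is missing. If missingness at the last visit depends on how a man was doing at midpoint, a likelihood model that includes both visits can adjust for it, and the single-visit regression cannot.

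**Working it through.** **1. Does the model need fixed timing?** No. A factor gives each nominal visit its own mean. An unstructured matrix gives each visit its own variance and each pair of visits its own covariance. Compound symmetry uses one common covariance. None of these contains a calendar date. The SAP itself pools the final IMRT visit across men as one nominal visit in the Rank-Sum test, the regression and the perineal-healing summary (SAP 10.3.6.2).

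**2. Is the midpoint any more fixed?** No. Protocol 2.2.6.7.2 leaves the dose-fractionation schedule to the site. Protocol 2.2.4 requires a dose equivalent to 78-81 Gy in 1.8-2 Gy fractions:

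- 78/2 = 39 fractions; 81/1.8 = 45 fractions.
- At five fractions a week (assumed), 7.8 to 9.0 weeks, so the midpoint falls at about 3.9 to 4.5 weeks, and earlier on shorter equivalent schedules.
- A midpoint EPIC is collected only if the plan exceeds one month.

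**3. How much does the exclusion cost?** The documents give no SD, effect, correlation or power for EPIC, so there is no plan figure to reproduce. The relevant figures they do give are 148 balloon and 74 control subjects, and 8% dropout at 6 months (about 12 of 148 and 6 of 74). Assumptions: SD 15, true difference 5 points in favour of the balloon, equal correlation of 0.4, 0.6 or 0.8 among baseline, midpoint and final scores, and a midpoint score for every man.

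Two estimates of the final-visit group difference were compared over 1,500 simulated trials per scenario:

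- *Regression:* final score on group and baseline, men with a final score only.
- *Joint likelihood:* b_G + b_M × a_G. Here b_G and b_M are the group and midpoint coefficients for the final score among men who have one, and a_G is the group coefficient for the midpoint score, given baseline, in all men.

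Results with 8% missing at the final visit (bias in points):

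| Correlation | Missingness | No data missing | Regression | Joint | Variance ratio, regression/joint |
|---|---|---|---|---|---|
| 0.4 | at random | -0.02 | -0.02 | -0.01 | 1.007 |
| 0.4 | low midpoint, same rule in both arms | 0.05 | -0.06 | 0.04 | 1.007 |
| 0.4 | unequal | 0.03 | -0.60 | 0.01 | 1.014 |
| 0.6 | at random | 0.11 | 0.10 | 0.11 | 1.012 |
| 0.6 | low midpoint, same rule in both arms | 0.04 | -0.08 | 0.04 | 1.000 |
| 0.6 | unequal | -0.04 | -0.65 | -0.02 | 1.009 |
| 0.8 | at random | -0.06 | -0.06 | -0.07 | 1.009 |
| 0.8 | low midpoint, same rule in both arms | 0.02 | -0.04 | 0.04 | 1.023 |
| 0.8 | unequal | -0.01 | -0.46 | -0.02 | 1.032 |

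Unequal means 16% missing in control, driven by low midpoint scores, and 4% at random in the balloon arm; the average is (74 × 0.16 + 148 × 0.04)/222 = 8%. The no-data-missing column shows the simulation noise (standard error about 0.03 to 0.06).

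- *Same rule in both arms:* bias is -0.04 to -0.08. Net of the no-data-missing column it is -0.06 to -0.12, so about 0.1 point.
- *Unequal:* bias is -0.46 to -0.65 points, or 9% to 13% of the assumed difference (0.46/5, 0.65/5), and about a third of the estimate's own SD (0.65/1.845 = 0.35). The sign is against the balloon.
- *More extreme (30% vs 7.5%, average 15%):* -0.82 to -1.28 points.

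**4. Cross-check on precision.** With missing share m and midpoint-to-final correlation r after adjusting for baseline, the variance ratio is about 1 + r² × m/(1-m). Under equal correlation ρ, r = ρ/(1+ρ), which is 0.286, 0.375 and 0.444. With m = 0.08 the ratio is 1.007, 1.012 and 1.017, in line with the simulated 1.00 to 1.03.

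**The case against.** The strongest reply is that little depends on this model. The SAP lists the Rank-Sum tests first and introduces the mixed model as an addition. The Protocol's labelling test for EPIC is itself a single-visit Rank-Sum test, which the fix does not touch. Neither document rests a claim on the mixed model's Type III tests. With complete data, the regression and a mixed model with baseline-by-visit terms give the same final-visit difference. The separate regression also has a merit: it does not depend on the covariance structure, whereas a joint estimate would if the fallback were used. The 8% is a 6-month figure, and fewer men would normally be missing on a treatment day. Men on plans of a month or less have no midpoint score to borrow from. Finally, Protocol 2.3.4.5 lists no visits, and that the midpoint is in the SAP's model is itself an inference. All of this stands. It limits the size of the point, but it does not rescue the stated reason.

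Two stronger readings should be resisted. A reader might infer that the end of treatment is analysed on study completers only. It is not: the regression takes Per-Protocol men with scores at baseline and at that visit, so a man lost between radiotherapy and 6 months is included. A reader might also infer that end-of-treatment toxicity goes untested. It is tested twice in each domain.

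**Conclusion.** The rationale in SAP 10.3.5.1 is wrong for the model described there. The exclusion leaves the repeated-measures model without end-of-treatment data, and SAP 3.2 does not declare this departure from the Protocol's by-visit model. The remaining analyses of that visit are observed-case, make no use of the midpoint score, and have no planned missing-data sensitivity analysis.

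The practical cost is small: at 8% missing, up to 3% in variance and about 0.1 point of bias on a 0-100 scale when one missingness rule holds in both arms. It reaches about 0.5 to 0.65 points only with clearly unequal missingness, which the documents give no reason to expect. These figures rest on the assumed SD, difference, correlations and missingness patterns, and the gain applies only where a midpoint score was taken. This is an inexpensive improvement, not a threat to the trial's conclusions.

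**What to change.** In SAP 10.3.5.1:

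- List the visits in the mixed model and make the final IMRT visit a level of the visit factor.
- Add baseline-by-visit terms and report the end-of-IMRT group difference from the least-squares means at that level.
- Delete the sentence that rules the visit out.
- Keep the separate regression, which does not depend on the covariance fallback, and the Rank-Sum tests.

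Record the change in SAP 3.2. The cost is SAP wording and one more visit level, with the same data and the same procedure. The unstructured matrix gains parameters: going from three to four visits, for example, raises the count from 3 × 4/2 = 6 to 4 × 5/2 = 10. If that forces the fallback, the retained regression is the check on the joint estimate.

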#### *Change in EPIC = Baseline EPIC + Group*

The residuals of all linear or mixed model will be evaluated to consider the degree to which the data appear to be normally distribution.

### 10.3.5.2 Secondary Efficacy Endpoints

Additional dosimetry parameters ( $D_{Rectum}100$ ,  $D_{Rectum}90$ ,  $D_{Rectum}80$ ,  $D_{Rectum}70$ ) will be evaluated in the *ProSpace Group* only, where subjects will serve as their own control (dosimetry reduction after balloon implantation) since the dosimetry parameters are compared to their baseline values per subject.

The distance of the rectal wall from the prostate, as evaluated by the core lab, will also be summarized at baseline and last XRT visit.

All secondary efficacy endpoints are numeric. If change from baseline is approximately normally distributed (or normalized transformation can be identified), the endpoint will be tested using the following regression.

#### *Change from baseline = Baseline.*

If an endpoint distribution deviates strongly from a normal distribution, a non-parametric 95% confidence interval for median will be calculated, using percent change from baseline (to account for baseline impact). The Sign-Rank test will be provided for change from baseline comparisons where appropriate to evaluate the null hypothesis that the difference is equal to zero.

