2.2.6.2 VISIT WINDOWS

- Pre-implantation windows vary from 2 to 30 days.
- Post-implantation imaging no sooner than 3 days post implantation and sufficiently prior to planning to allow time for image processing.
- IMRT planning must occur after imaging and no later than 21 days post marking.
- IMRT treatments must begin no more than 24 days after marking/ implantation.
- Weekly data recording has no window.
- Follow-up at the 6 months window is ± 2 weeks.
- Follow-up for all subsequent visits is ± 4 weeks.

2.2.6.3 **CTs**

CT will be taken for the *Balloon Group* up to 30 days pre-implantation, post-implantation, at the last XRT visit and at the 6-month F/U visit. Additionally, CT may be taken in the Balloon Group at 12 months if remnants of the balloon remain at 6 months.

A CT will be taken in the *Control Group* post-implantation.

Group	Up to 30 Days Pre-Implantation	Post- Implantation	Last X-RT	6 Mo	12 Mo (if needed)
Balloon	Х	Х	Х	Х	X
Control		Х			

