## **3.2** Changes to Planned Analyses

Review of the statistical analysis plan identified that windowing is not required to capture events in the first 6 months since the events are classified based on the onset date. Hence, the primary safety analysis would be more accurate if based on events through Day 183 (6 months). The primary safety analysis was updated to reflect this change and the protocol specified cut-off based on 197 days was moved to be a sensitivity analysis. The following changes are reflected in the SAP:

- Section 10.3.4.1.1 now states that the primary safety analysis will include events from marking through Day 183 (6 months). Section 10.3.4.1.3 has been updated to include a sensitivity analysis for the primary safety endpoint from marking through Day 197.
- It has also been clarified in Section 10.3.4.1.3 that the sensitivity analysis using the Kaplan-Meier method will provide estimates for the proportion of subjects experiencing AEs of interest through Day 183.

In addition, Section 10.3.4.1.1 now describes how the primary safety endpoint will be determined through CEC adjudication and clarifies that events related to anesthesia or to the use of a foley catheter will not be considered marking or implantation procedure-related.

It has been clarified in Section 10.3.5.1 that the secondary EPIC safety endpoint will be evaluated for four domains: Urinary Incontinence, Urinary Irritative, Bowel, and Sexual.

Section 10.3.5.2 clarified that the Sign-Rank test would be used for a within-group paired difference comparison.

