# **10** Statistical Methods

## **10.1 General Statistical Considerations**

Study data will be made available in listings or electronic files, and study data will be listed by subject with the randomized treatment indicated. The study results will be summarized using descriptive statistics by randomized treatment. Summaries of baseline information will also include a total column. Standard numeric descriptive statistics include the n (observed values), mean (including the 95% confidence interval), standard deviation, median, minimum, and maximum values. Categorical data will be summarized with counts and percentages calculated based on non-missing values. Measures summarized across multiple visits will be summarized by visit, and a change from baseline will be provided for numeric variables.

A two-sided p-value of less than or equal to 0.05 or a one-sided p-value of less than or equal to 0.025 will be considered statistically significant unless otherwise specified.

All statistical analyses and summaries will be generated using SAS version 9.4.

<sup>1 HHS, FDA (1998). Guidance for industry: E9 Statistical Principles for Clinical Trials

<sup>2 SAS software. Version 9.4. Copyright © 2016 SAS Institute Inc., Cary, NC, USA.

Statistical Analysis Dlan	Client/Project	BioProtect BP-007
Statistical Allalysis Flan	Version and Date	V2 05-DEC-2021

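### The regression of change on baseline that SAP 10.3.5.2 uses to test the single-arm secondary efficacy endpoints does not test mean change, and no rule says which planned result decides

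*SAP*

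**What the plan says.** SAP 10.3.5.2 covers D_Rectum100, 90, 80 and 70 and the rectal wall to prostate distance. The dosimetry parameters are evaluated in the ProSpace Group only, each man being his own control. SAP section 12 tabulates both sets for the ProSpace Per-Protocol Population (Tables 14.2.1.5 and 14.2.1.6).

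If change from baseline is approximately normal, or can be made so by transformation, "the endpoint will be tested using the following regression": "Change from baseline = Baseline". The section names no coefficient, centring, least squares mean or null hypothesis for this model, and no criterion for approximate normality. If the distribution departs strongly from normal, a non-parametric CI for median percent change replaces it.

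The section then adds: "The Sign-Rank test will be provided for change from baseline comparisons where appropriate", with a zero difference as the null. SAP 3.2 is firmer: "Section 10.3.5.2 clarified that the Sign-Rank test would be used for a within-group paired difference comparison". SAP 10.1 includes a 95% CI for the mean among its standard descriptive statistics and says that "a change from baseline will be provided for numeric variables" where a measure is summarised over several visits.

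Protocol 2.3.4.5 gives a different method for the same endpoints: "These are all numeric measures and will be compared between groups using Rank-Sum tests". Protocol 2.2.6.3, however, allows controls a single scan: "A CT will be taken in the *Control Group* post-implantation".

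**The concern.** In a one-sample, before-and-after comparison the question is whether mean (or median) change differs from zero. A regression of change on uncentred baseline answers two other questions. The intercept asks what change to expect in a man whose baseline is zero. The slope asks whether change varies with baseline, and it absorbs regression to the mean. The EPIC regression in SAP 10.3.5.1 has the same form plus a Group term, and there Group is the term of interest. Without Group, nothing left in the model is the quantity wanted.

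So the result labelled as the test could miss a real reduction, or be significant when mean change is zero. It would stand beside a valid Sign-Rank p-value and a valid CI, with no written rule for which one counts. The protocol's Rank-Sum test does not settle this. Controls have no pre-implantation CT, so a between-group comparison of change cannot be made. SAP 3.2 mentions Sign-Rank but neither lists the regression as an added analysis nor says that Rank-Sum is replaced.

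**Working it through.** **Plan's own figure.** The documents give no power, mean, SD or correlation for these endpoints. The only figure that can be checked is the one behind the sample size used here, the 136 evaluable balloon subjects of Protocol 2.3.4.4.1. For the exact binomial test of 75% against 87.5% at one-sided 0.025, success needs at least 113 of 136. Attained alpha is 0.0159 and power 0.949, in line with the stated 95%.

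**What the model estimates.** With change = a + b × baseline + error, mean change is a + b × (mean baseline). It equals a only if mean baseline or b is zero. It never equals b in general.

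**Illustration.** All inputs except n=136 are assumed: baseline mean 10, SD 1, two-sided 5%, 10,000 simulated trials per setting.

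*(i) Real proportional reduction.* Post = pre × ratio, with mean ratio 1 − red. Take red = 0.25 + 1.150 × (ratio SD), so that 87.5% of men fall by at least 25%. This rate is borrowed from the V70 planning assumption.
- Ratio SD 0.10: red = 0.25 + 0.115 = 0.365.
- Ratio SD 0.15: red = 0.25 + 0.1725 = 0.4225.

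Expected change is −red × pre, so the true intercept is 0 although mean change is about −3.65 or −4.2.

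| Ratio SD | Intercept | Slope | Paired t | Sign-Rank |
|---|---|---|---|---|
| 0.10 | 4.8% | 98% | 100% | 100% |
| 0.15 | 4.7% | 89% | 100% | 100% |

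Shapiro-Wilk at 5%, used as a stand-in because the SAP sets no rule, rejects normality of change in only 11% and 10% of trials. Most such data would therefore stay in the regression branch. Among trials that pass, the intercept still rejects in 4.8% and 4.6%.

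*(ii) Zero mean change with regression to the mean.* Pre and post are bivariate normal, both with mean 10 and SD 1, correlation ρ. Then b = ρ − 1, a = 10(1 − ρ) and residual SD = √(1 − ρ²). The standard errors are SE(b) = √(1 − ρ²)/√136 and SE(a) = √(1 − ρ²) × √(101/136). For ρ = 0.9:
- b = −0.1, SE 0.4359/11.66 = 0.0374, ratio 2.68.
- a = 1.0, SE 0.4359 × 0.862 = 0.376, ratio 2.66.
- Approximate rejection rate Φ(2.66 − 1.96) = 76%.

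| ρ | Intercept (simulated) | Slope (simulated) | Paired t | Sign-Rank |
|---|---|---|---|---|
| 0.95 | 44% | 45% | 4.7% | 4.8% |
| 0.9 | 75% | 75% | 5.3% | 5.1% |
| 0.8 | 96% | 97% | 4.8% | 4.9% |

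The significant intercept is always positive, an apparent increase.

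*(iii) Uniform shift.* With every man's expected fall equal to 3 and independent noise of SD 1 (5,000 trials), the slope rejects in 5.3% and the paired tests in 100%. The slope is thus blind to a uniform benefit, as the intercept is to a proportional one.

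**Where the problem shrinks.** With purely proportional noise around no change (ratio SD 0.10), both coefficients reject near 5%. If the model is reported as a least squares mean at average baseline, rejection is 5.1%, 5.9% and 6.0% in (ii) and 100% in (i).

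**The case against.** The strongest reply is that the SAP already names a valid test. SAP 3.2 assigns the within-group paired comparison to Sign-Rank without qualification, and SAP 10.3.5.2 gives that test the only explicit null hypothesis for these endpoints. The regression could then be read as a baseline-adjusted supplement, leaving only a drafting gap. The table shells are in a separate document and may report a least squares mean, as the EPIC mixed model does, which would nearly remove the problem.

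The sizes also depend on the inputs. Setting (i) fixes the true intercept at zero. With a uniform shift of −3.65 the intercept rejects in 100%, 98% and 80% at residual SD 0.5, 1 and 1.5. For distance, an assumed baseline of 3 (SD 1) and change of +10 (SD 3) gives 100%. In (ii) the intercept points to an increase, so it could not support a false claim of reduction. Finally, no decision rule uses these endpoints.

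The points on inputs, direction and limited consequence stand. The first does not remove the concern. SAP 3.2 neither mentions nor withdraws the regression, while the operative section makes the regression the test and leaves Sign-Rank to an undefined condition. Least squares means are specified only for the EPIC mixed model.

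**Conclusion.** The concern holds. In the roughly normal branch, the SAP prescribes as the test a model whose default coefficients do not address mean change, and it does not say that the valid results it also plans take precedence. This mismatch of hypotheses follows from the model alone and needs no assumed numbers.

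Its size does depend on assumptions. Rejection by the intercept ranges from about 5% under a large real proportional effect to 96% under no mean change at correlation 0.8. Those figures rest on an assumed baseline CV of 0.1, a borrowed response rate in (i) and regression to the mean in (ii). Other plausible patterns give correct answers. The impact is confined to secondary efficacy reporting. The co-primary success rule, the labelling tests at 0.0167 and the sample size and power are untouched. It should be corrected before database lock, but it does not threaten the trial's main conclusion.

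**What to change.** In SAP 10.3.5.2, make the Sign-Rank test of within-subject change against zero the single deciding test for every single-arm secondary efficacy endpoint, whatever the distribution, and remove the qualifier that makes it conditional. Report mean or median change with its 95% CI. Label the regression on baseline as descriptive. In SAP 3.2, state that this replaces the between-group Rank-Sum test of Protocol 2.3.4.5.

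This needs two or three sentences and no new data. The cost is a small loss of efficiency if change is exactly normal: at n=136 and a standardised change of 0.242, power is 78.0% for Sign-Rank against 79.8% for the paired t (20,000 simulated trials). The Sign-Rank result reads as a median shift only if changes are roughly symmetric. A paired t-test would also answer the right question; what matters is that one test of change is named in advance as deciding.

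### The SAP's non-normal fallback puts prostate-rectum distance on a percent-change scale that depends mainly on the baseline; change in mm fits the endpoint and the planned Sign-Rank test better.

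*SAP*

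**What the plan says.** The protocol (2.3.4.5) lists as a secondary efficacy endpoint: "Core lab evaluation of distance of rectal wall from the prostate at baseline and last XRT visit". SAP 10.3.5.2 carries it forward beside the rectal dose parameters: "The distance of the rectal wall from the prostate, as evaluated by the core lab, will also be summarized" at those two visits.

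The SAP then treats the endpoints as one class ("All secondary efficacy endpoints are numeric") and gives a two-step rule.

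- First step: "If change from baseline is approximately normally distributed (or normalized transformation can be identified", the change is regressed on baseline.
- Fallback: "If an endpoint distribution deviates strongly from a normal distribution", the result is "a non-parametric 95% confidence interval for median will be calculated, using percent change from baseline (to account for baseline impact".

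The same paragraph adds a Sign-Rank test on change from baseline, with a null difference of zero. Distance is not exempted from the fallback, and nothing is said about a zero denominator. SAP 10.1 bases summaries other than the co-primary analyses on observed data with nothing imputed.

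The one distance criterion in the documents is in millimetres and applies with the balloon in place (protocol 2.2.6.7.2): "For *Balloon Group* verification of spacing status as at least 10 mm (from prostate to rectum".

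**The concern.** Percent change suits the dose parameters. They are expected to fall from baseline, and the primary efficacy criterion is itself a percent reduction. Distance behaves differently: the device exists to create space, so the value should rise from whatever small gap is there before implantation. Three difficulties follow if the fallback is used for distance.

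- With a small denominator, the statistic mostly reflects how small the baseline was, although the stated reason for using it is to account for baseline.
- A man with baseline 0 has no percent change. The SAP does not say whether he is dropped or ranked highest. Under the observed-data rule in SAP 10.1 the natural reading is that he is dropped.
- The interval and the test describe different quantities. A zero-baseline man counts in the Sign-Rank test but not in the interval.

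At stake is the clarity of one secondary, within-group result. It bears on whether space is still held at the last radiotherapy visit, whereas the SAP assesses the primary efficacy endpoint at 21 days after implantation.

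**Working it through.** **Plan's own figure.** The documents give no expected distance, SD or power for this endpoint, so there is nothing to reproduce. The only sample size needed is the 136 evaluable balloon subjects (protocol 2.3.4.4; SAP section 6).

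**Step 1: single subjects.** Percent change = 100 × (final − baseline) / baseline. For an assumed final distance of 12 mm:

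| Baseline (mm) | Change (mm) | Percent change |
|---|---|---|
| 5 | 7 | 100 × 7/5 = 140% |
| 1 | 11 | 100 × 11/1 = 1100% |
| 0 | 12 | not computable |

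**Step 2: share with baseline 0.** Assume (not in the documents) a normal baseline with mean m and SD s, truncated at 0 and recorded to the nearest mm. The share recorded as 0 is [Φ((0.5 − m)/s) − Φ(−m/s)] / [1 − Φ(−m/s)].

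- m = 2, s = 2: (0.2266 − 0.1587)/0.8413 = 8.1%, about 11 of 136.
- m = 3, s = 2: (0.1056 − 0.0668)/0.9332 = 4.2%, about 6 of 136.
- m = 5, s = 3: (0.0668 − 0.0478)/0.9522 = 2.0%, about 3 of 136.

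The share depends heavily on the assumption. Setting negative draws to 0, instead of truncating, gives 7% to 23%. Truncating but recording to 0.1 mm gives 0.2% to 0.7%.

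**Step 3: what the fallback would report.** This is a simulation with the Step 2 baselines (truncated, 1 mm) and an independent last-XRT distance of mean 12 mm, SD 4.

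| Baseline mean/SD (mm) | Median % change, zeros dropped | Median % change, zeros ranked highest | Median change (mm) |
|---|---|---|---|
| 2/2 | 356% | 393% | 9.5 |
| 3/2 | 263% | 276% | 8.7 |
| 5/3 | 126% | 130% | 6.7 |

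Among men with a non-zero baseline, percent change has a Spearman correlation of about −0.8 with baseline and about +0.5 with final distance. It orders men more by where they started than by the space they ended with. Any zero-baseline men who are dropped have the larger average gain: 12.0 mm, against 6.6 to 9.2 mm for the rest.

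**Step 4: no zeros needed.** Take n = 136, a final distance of mean 15 mm (SD 4), and uniform baselines with no zeros (all assumed).

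| Baseline range (mm) | Median % change (95% CI) | Median change, mm (95% CI) |
|---|---|---|
| 3 to 7 | 199% (178 to 224) | 10.0 (9.1 to 10.8) |
| 1 to 4 | 500% (442 to 567) | 12.5 (11.6 to 13.4) |
| 0.1 to 2 | 1333% (1144 to 1600) | 14.0 (13.1 to 14.8) |

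The percent result moves nearly sevenfold (1333/199 = 6.7) and the mm result by a factor of 1.4 (14.0/10.0). Protocol 2.2.4 allows CT slices up to 2 mm thick, comparable to the smaller denominators.

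**Step 5: does the median stay defined?** At n = 136 the order-statistic 95% CI for a median runs from rank 57 to rank 80. With zero-baseline men ranked highest, rank 80 is infinite only if at least 137 − 80 = 57 men have baseline 0 (57/136 = 42%). The median, the average of ranks 68 and 69, is infinite only if at least 137 − 69 = 68 do (50%). The assumed 2% to 8% is far below both.

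**Step 6: would the fallback be reached?** In the Step 3 scenarios the change in mm is close to normal: skewness is within 0.06 of zero, and Shapiro-Wilk rejects in about 4% to 5% of samples of 136. Such data would go to the regression on mm change. The percent figures show what the fallback would report if used, not what these scenarios would lead to.

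**The case against.** The strongest reply is that the plan already gives the mm result. SAP 10.1 calls for by-visit summaries and change from baseline for numeric measures, and includes a 95% interval for the mean. Table 14.2.1.6 is reserved for rectal wall distance. The Sign-Rank test is on change, so no man is lost from it through a zero denominator. The percent-change interval comes only after regression and a search for a transformation have failed. The endpoint is within-group and outside the labelling tests in SAP 10.2. All of this stands, and it keeps the point minor.

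A reader might infer more than the documents support:

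- That baseline distance is zero or near zero in this population. No baseline value appears anywhere, and the 10 mm figure applies with the balloon in place.
- That the reported estimate is undefined or explodes. That is true of individual ratios; Step 5 shows the median and its interval are robust to the assumed share of zeros.
- That the SAP orders zero-baseline men to be excluded. It is silent, and dropping them is only the natural reading of its observed-data rule.
- That distance would be left without an interpretable result. The mm summaries contradict this.

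What the reply does not answer is why the fallback for this endpoint should use a scale that differs from the planned test, has no zero rule and depends mainly on the denominator.

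**Conclusion.** The concern holds as a minor misfit of a stated rule. As written, the percent-change fallback covers prostate-rectum distance, where it is governed chiefly by baseline size, cannot be computed from a baseline of 0, and is not the quantity the Sign-Rank test addresses.

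The size rests wholly on assumed baselines. Under those in Step 2, 2% to 8% of men would lack a value, and the median percent change would vary almost threefold (126% to 356%) while the median change in mm varied from 6.7 to 9.5. The result also assumes that final distance is independent of baseline. No co-primary result, error rate or labelling claim is affected.

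**What to change.** Add one sentence to SAP 10.3.5.2: for prostate-rectum distance, the non-parametric estimate and 95% CI are for change from baseline in mm (Hodges-Lehmann, which inverts the Sign-Rank test), and percent change is kept for dose parameters with a non-zero baseline.

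Hodges-Lehmann estimates the pseudo-median, which equals the median when the changes are symmetric. If marked skewness is expected, the order-statistic interval for the median change in mm can be shown beside it.

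The cost is that sentence, with Table 14.2.1.6 adjusted if its shell shows percent change. No new data or visits are needed. Settling it before analysis removes a later choice between dropping and ranking zero-baseline men.
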